### **5. Vulnerable Populations**

Children (under age 18), pregnant women or prisoners are not included in this research study.

### **6. Populations vulnerable to undue influence or coercion**

Educationally or economically disadvantaged persons are included but not solely targeted for recruitment. Cognitively impaired persons are not included in the current study. Because of our recruitment efforts for this study, it is possible that University of Pennsylvania employees and students may be invited to participate but will be neither targeted nor excluded from participating in this study. Status of participation in the current study will be voluntary and independent of the participants work or school activities. The decision of whether or not to participate in the research study will not impact employee or student standing with the University of Pennsylvania.

### **7. Subject Recruitment**

Participants may be recruited from the Adult ADHD Treatment and Research Program, ADHD discussion boards, study brochure, TV/radio advertisements, patient mailings, Craigslist.org/Internet advertisements, Experiments@penn, flyers, and/or from our database of previous participants who have agreed to be re-contacted for future studies. Interested participants that complete online questionnaires will be given the option to be contacted via email or text message to schedule a time to complete a telephone screen to assess initial eligibility. Interested participants will complete a telephone screen to assess initial eligibility. Those who are initially eligible will be screened against our registration database to confirm that they are not currently participating in another research study at our Center and have not previously reported a condition or circumstance that would make them ineligible for the current study. They will then attend an Intake Visit during which the purpose and procedures of this study will be described to them and final eligibility will be confirmed.

### **8. Real time safety monitoring**

TMS will be administered by appropriately trained personnel and under the supervision of a physician experienced in neuromodulation. Initial motor threshold (MT) determination, targeting for coil placement, and initial determination of treatment parameters will be overseen by the study physician. The study physician will participate in the evaluation of tolerability and response during the TMS course and will be available on site or within a short commute. Subjects will be monitored at all times during TMS for side effects including involuntary motor activity and a protocol for seizure management will be in place. Equipment will also be monitored during sessions with respect to the settings for stimulus intensity (measured in % motor threshold), coil placement, and coil temperature.

## **STUDY DESIGN**

### **1. Phase**

Not applicable

### **2. Design**

This trial will use a between-subject double blind design in which TMS dosage (active or sham) will be randomly assigned. Eligible participants will complete an **Intake Visit (week 0)** for final eligibility determination. Eligible participants will complete an additional 20 study visits

(5 visits per week for 4 consecutive weeks) during which they will receive 26-minute sessions of TMS. Participants will complete a series of computerized cognitive assessments prior to initiating the TMS period (Baseline) and will complete the same series of computerized cognitive assessments after their final TMS session (Session 20).

### **3. Study Duration**

Enrollment will begin in January 2017. Based on the accrual projections described previously, we anticipate enrollment lasting through March 2019. Each participant will be required to be in the study for approximately 4-6 weeks.

## **DRUGS OR DEVICES**

Transcranial magnetic stimulation (TMS) and sham stimulation.

## **STUDY PROCEDURES**

### **1. Procedures**

**Telephone Screening:** Potential participants will be screened by an experienced research technician to determine initial study eligibility. The 6-item Adult ADHD Self-Report Scale (ASRS) will be administered during the phone screen. If the subject meets preliminary telephone eligibility criteria he/she will be invited to attend an Intake visit.

**Visit Reminders:** Participants will receive study visit reminders 24 – 48 hours prior to their scheduled study visits via phone call, email or text (participants who provide a cell phone number for contact). No sensitive information about subjects will be included in electronic reminders.

**Intake (week -1):** (Visit duration 3-3.5hrs) Participants will:

1. Hear a study description where all study procedures will be reviewed. Participant questions will be answered. Following this presentation, the combined informed consent and HIPAA form will be completed;
2. Complete a urine drug screen (at least 30ml [two tablespoons] of urine). The urine drug screen will assess the use of any study-prohibited medications/recreational drugs (See Key Exclusionary Criteria; Alcohol/Drugs). Participants who test positive for any exclusionary medications or recreational drugs will be deemed ineligible.
3. Self-administer a CLIA-approved urine pregnancy test (female participants of child bearing potential only). Participants are advised that we do not recommend participation for pregnant women, and that they may withdraw at any time without penalty;
4. Perform a BrAC assessment to control for alcohol consumption. Participants with a BrAC greater than or equal to 0.01 at Intake Visit will be ineligible;
5. Complete a carbon monoxide (CO) breath assessment (smokers only) to control for smoke exposure;
6. Complete a brief medical history form with a trained staff member;
7. Complete Structured Clinical Interview for DSM-5 (SCID);
8. Complete Shipley Institute of Living Scale (SILS) IQ test. Participants earning less than an estimated WAIS-R IQ score of 90 will be ineligible;
9. Complete demographics and smoking history (smoking rate, nicotine dependence) and paper and pencil questionnaires (mood, QIDS, CAARS:S-L & ASRS).

**Baseline (week 0):** (Visit duration 1.5hrs) Participants will:

1. Urine drug screen. See key exclusionary criteria; Alcohol/Drugs;
2. Pregnancy screen (females of child bearing potential only);
3. BrAC assessment. See breath alcohol concentration under screening/covariates for exclusionary criteria;

4. Provide information regarding recent nicotine and caffeine intake, and any medication changes since the Intake visit;
5. A carbon monoxide (CO) breath sample (smokers only);
6. Complete paper and pencil questionnaires (POMS);
7. Complete computerized cognitive tasks which may include assessments of working memory, sustained attention, risk aversion, delay discounting or reaction time.

**TMS Sessions (Sessions 1 - 20):** (Visit duration ~1-2hrs). The stimulation protocol is adapted from TMS Investigations of Cognition and Motor Function, which was employed in The Laboratory for Cognition and Neural Stimulation (LCNS).

Participants will complete the following during Sessions 1 - 20:

1. Urine drug screen (Sessions 1, 5, 10, 15 & 20). See key exclusionary criteria; Alcohol/Drugs;
2. Pregnancy screen (females of child bearing potential only) (Sessions 1, 5, 10, 15 & 20);
3. BrAC assessment. See breath alcohol concentration under screening/covariates for exclusionary criteria;
4. Assessment of recent nicotine and caffeine intake, and any medication changes since last assessment (Sessions 1, 5, 10, 15 & 20);
5. TMS safety & side effects questionnaire;
6. A carbon monoxide (CO) breath sample (smokers only);
7. Complete paper and pencil questionnaires;
8. Receive 26 minutes of TMS (active or sham);
9. Complete computerized cognitive tasks which may include assessments of working memory, sustained attention, risk aversion, delay discounting or reaction time (Sessions 5, 10, 15 & 20).

**Attendance:** Participants will be asked to attend all study visits. Participants attending less than 4/5 visits during the first two weeks or less than 3/5 sessions in the final two weeks of the study will be excluded.

**TMS Training Procedures:** Prior to each TMS session an investigator or trained research assistant will review the procedures, goals, risks, and potential benefits of the study and confirm that no change has occurred affecting study inclusion and exclusion criteria. The TMS sessions will be conducted by a trained TMS clinician using the The MagPro R30 (Magventure, Inc., Copenhagen, Denmark) device with a figure 8 coil. During Sessions 1 - 20 participants will receive 26 minutes of sham or active TMS using the parameters described below. Participants will be blind to condition.

**Active TMS:** A MagPro R30 (Magventure, Inc., Copenhagen, Denmark) device with a Cool-B65 A/P figure 8 coil will be used to deliver TMS. This coil has an active side and a sham side, and can be used to perform double-blinded studies. The MagLink software program is used to define the treatment protocol for each participant. This includes defining whether a given patient is to receive real or sham treatment. When the protocol has been defined it is downloaded to a Patient Key (which must be inserted into the device in order to deliver stimulation. The Cool-B65 A/P coil has a built-in position sensor used to ensure that the correct (active or sham) side of the coil faces towards the participant's head. If the coil position is wrong, a "Flip Coil" prompt will be displayed on the MagPro screen.

We will use a TMS paradigm which has been successfully and safely utilized in other studies of rTMS at the University of Pennsylvania. In this paradigm, brief trains of moderately rapid stimulation are presented for a short period of time. In light of the demonstrated utility of the

brief train technique in conjunction with an excellent safety record, we propose to deliver brief trains of stimulation.

To control for inter-participant variability in sensitivity to TMS, a motor threshold will be established for each participant at the beginning of each week of TMS. Motor threshold is defined as the lowest intensity at which a single pulse of TMS over the contralateral hand representation elicits a visible motor response of the hand. The hand representation is typically identified as the omega or epsilon shaped section of the motor cortex.

TMS will be administered at 10Hz with an intensity of 120% of patient resting motor threshold. Stimulation will be delivered to the left dorsolateral prefrontal cortex using 20 sec cycles (i.e., 5 sec train with 15 sec inter train interval). Subjects will receive 80 trains per session for a total of 4000 pulses per session (~26 min sessions). These settings are considered high dose and we intend to use them to increase the chances of patient clinical benefit and treatment compliance and to reduce the risk of lack of efficacy due to unnecessarily conservative dosing. Although these parameters differ from the set parameters described in Rossi et al., 2009, they are still in line with safety recommendations for motor cortex of healthy subjects including ITI >5 (more than twice as long as the active stimulation time in this case) and are consistent with what has been published as being safe (no induction of seizures) and effective when used to stimulate non-motor cortex (i.e., dorsolateral prefrontal cortex) of patients with major depressive disorder taking medications that may decrease seizure threshold (Connolly et al., 2012; Hadley et al., 2011). The proposed ITI also complies with the 2016 FDA label modification that allows a range of inter-train intervals from 11-26 seconds when using TMS in clinical settings (Food and Drug Administration, 2016). To further increase the margin of safety in this protocol we are excluding patients taking medications known to decrease seizure threshold and we will use ~40% less pulses per session than what is considered safe in the literature (Hadley et al., 2011). The Beam-George EEG F3 system for location of the stimulation target will be used in conjunction with personalized patient caps to increase consistency in coil placement.

Sham TMS: Sham TMS will utilize the same procedures as above, except that the sham side of the coil will be positioned toward the participant's scalp. The sham coil is designed to mimic the appearance and sound of active tDCS stimulation, but is equipped with a magnetic shield that reduces the strength of the field by approximately 80%. This reduction in field strength ensures that no neural stimulation occurs (Duecker and Sack, 2015).

**Table 1. Measures and Time Points**

Activity	Intake	Baseline	TMS Sessions (1 - 20)
Weeks	-1	0	1, 2, 3 & 4
Urine Drug Screen	x	x	x 
Urine Pregnancy Screen	x	x	x 
BrAC	x	x	x
Carbon Monoxide (CO)	x 	x 	x 
Demographics	x		
ETOH History	x		
Smoking Behavior (FTND)	x 		
Caffeine & nicotine use	x	x	x 
Height	x		
Weight	x		
Medical History Form	x		
TMS safety checklist	x		x
ShIPLEY Institute of Living Scale (IQ)	x		
SCID-5	x		
Treatment			
TMS (active or sham)			x
Primary Outcomes			
CARRS: S-L	x	x	x 
ASRS	x	x	x 
Secondary Outcomes			
PASAT		x	x 
Continuous performance task		x	x 
Risk Task		x	x 
QIDS	x	x	x 

 Smokers reporting having smoked in the past 24hrs.

 Administered at sessions 1, 5, 10, 15 & 20.

 Administered at sessions 1, 5, 10, & 15.

 The cognitive battery & ADHD clinical measures will only be administered at TMS sessions 5, 10, 15 & 20.

**Back-up scheduling for Session 1 visits:** Since we are limited in the number of study tracks we are able to run per week we are also offering the opportunity to become a back-up participant for Session 1 visits. Back-up participants will only be scheduled for a TMS session 1 visit (occurring on Mondays). Participants may only be a back-up if they have not yet initiated a TMS track (have not attended TMS Session 1). Becoming a back-up is completely voluntary and participants will not receive any extra stimulation sessions if they decide to become a back-up participant in this study. In order to be scheduled as a back-up participant the participant must agree to do the following:

- Show up for the scheduled Session 1 appointment at the designated time;
- Be available for all subsequent study track visits in the event that they are promoted to the primary participant (if the primary participant for that date does not attend their session or is deemed ineligible at the visit).

If the participant attends the Session 1 visit as a back-up participant and is not needed on that date they will not undergo any study procedures (will not receive any stimulation), they will be

compensated \$25 for their time and will be free to leave. Back-up participants will then be scheduled for the next available study track as the primary participant.

If the primary participant for that session does not attend the visit or is otherwise deemed ineligible the back-up participant will be promoted to the primary participant and will start their study track. They will be compensated for their time in accordance with the usual payment plan.

### **1. Screening/Covariates:**

Adult ADHD Self-Report Scale (ASRS) – Screening version: The screening version of the Adult ADHD Self-Report Scale (ASRS) Version 1.1 is a 6-question scale designed to screen for adult ADHD in community samples. The ASRS was developed by a World Health Organization (WHO) work group in conjunction with the creation of the WHO World Mental Health (WMH) Survey Initiative version of the WHO Composite International Diagnostic Interview (WMH-CIDI). This will be administered at phone screen.

Urine Drug Screen: A urine sample will be collected at Intake, Baseline and Sessions 1, 5, 10, 15 and 20 to conduct a urine drug screen. The urine drug screen indicates whether the subject has recently taken any of the following drugs or medications: cocaine, PCP, amphetamines, methamphetamines, opiates, methadone, THC, and/or barbiturates. Participants with a positive urine drug screen for any substance listed above other than THC will be deemed ineligible. In an effort to remain CLIA-compliant, results from urine drug screening will not be shared with participants. Participants will be informed that the testing is for research purposes only and that they will be informed of their eligibility status, but not of the specific testing results.

Urine Pregnancy Test: At the Intake and once a week during the study (Baseline & TMS Sessions 1, 5, 10, & 15), participants will be supplied with a simple, CLIA-waived urine pregnancy screen and informed that pregnant women are not advised to participate in this research study. Participants will then be instructed to administer the pregnancy test independently and will inform study staff if they would like to continue participation after they have administered the pregnancy screen. Participants will be informed that there is no penalty for discontinuing participation at this point in the visit and that they will still receive travel reimbursement for the visit.

Breath Alcohol Concentration: The BrAC assessment will be administered at all sessions. The breath alcohol monitor is a handheld device that uses a disposable mouthpiece and reports the concentration of alcohol in exhaled breath. Any reading greater than 0.000 indicates alcohol consumption within the last 14 hours. Participants with a BrAC greater than or equal to 0.01 at the Intake Visit will be ineligible. Participants who have a BrAC reading greater than or equal to 0.01 at any visit listed above may be ineligible to continue with the visit and will only be rescheduled/allowed to proceed with the study at the discretion of the Principal Investigator.

ETOH History: ETOH history will be administered at the Intake Visit and will ask subjects about their alcohol consumption over the past 7 days.

Demographics: Standard surveys will collect demographics (e.g., age, education, race, and gender).

Smoking Behavior: Participants reporting having smoked in the past 24 hours will complete the 6-item Fagerstrom test for nicotine dependence (FTND; (Heatherton et al., 1991) and a smoking history assessment which includes age at first cigarette, age at regular (daily) smoking, and

current smoking rate. Number of cigarettes smoked in past 24 hours and time of last cigarette will be recorded at each visit.

*Caffeine and Nicotine use:* At intake, baseline and TMS visits 1, 5, 10, 15 & 20 recent caffeine and nicotine use data will be collected to monitor use of these stimulant substances.

*Carbon Monoxide (CO):* The CO monitor is a handheld device that uses a disposable mouthpiece, reports CO in parts per million (ppm), and takes about 5 minutes to administer. Carbon monoxide measurements will be collected from smokers at each visit as a biochemical verification of smoking exposure.

*Medical:* Height and weight will be measured and recorded. All participants will complete a medical history form with a trained staff member to review for all contraindications listed previously.

*Shipley Institute of Living Scale:* All participants will complete the Shipley Institute of Living Scale (SILS) at the Intake Visit. The scale consists of two subtests: a 40-item vocabulary test and a 20-item test of abstract thinking. The total administration time is 20 minutes (10 minutes per subtest). A trained member of the study staff will score the test. The SILS correlates with the Wechsler Adult Intelligence Scale-Revised (WAIS-R) Estimated IQ Test; those participants earning less than an estimated WAIS-R IQ of 90 will be ineligible. The SILS is considered a highly reliable assessment tool, with a good total score internal consistency (Cronbach's alpha=.92).

*TMS Safety Checklist:* This checklist will be administered at all Intake and all TMS sessions. The purpose of this checklist is to verify that participants are eligible to receive TMS and that there have been no changes to eligibility status throughout participation.

*Structured Clinical Interview for DSM-5 (SCID):* Diagnostic and Statistical Manual of Mental Disorders (DSM) is the standard classification of mental disorders used by mental health professionals in the United States and contains a listing of diagnostic criteria for every psychiatric disorder recognized by the U.S. healthcare system. This interview will be administered at Intake to help determine eligibility for the study (see exclusion criteria above: medical/neuropsychiatric).

**Treatment:** See description above under TMS.

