#### **4. Key Exclusion Criteria**

Subjects who present and/or self-report with the following criteria at any point during study participation will not be eligible to participate in the study:

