##### Medical/Neuropsychiatric:

1. Women who are pregnant, planning a pregnancy, and/or breast feeding. Women of childbearing potential will agree to use a medically accepted method of birth control throughout their participation in the study and will undergo a urine pregnancy test once a week (at intake, Baseline, Session 1, Session 5, Session 10, & Session 15). Women who self-report a condition which renders them unable to become pregnant (i.e.,

hysterectomy, surgical sterility, menopause, etc) will not be required to complete the pregnancy tests. By enrolling in this protocol women of childbearing potential agree to use a method of medically accepted birth control (diaphragm, cervical cap, condom and spermicide, surgical sterility, or birth control pills) for the duration of their participation.

2. History of seizures, epilepsy, or history of epilepsy in first-degree relative
3. History of stroke or transient ischemic attack (warning stroke)
4. History of traumatic brain injury or self-report of brain or spinal tumor
5. History of head injury with unconsciousness lasting more than 5 minutes
6. Previous brain surgery
7. Any additional neurological condition that would likely reduce the safety of study participation, including central nervous system (CNS) vasculitis, intracranial tumor, intracranial aneurysm, multiple sclerosis or arteriovenous malformations
8. History of tinnitus
9. History of diabetes mellitus
10. History of atherosclerotic vascular disease
11. A medically unstable cardiopulmonary or metabolic disorder
12. Increased risk for myocardial infarction or other major cardiopulmonary complications. (Exclusions include, but are not limited to, subjects with unstable angina, decompensated congestive heart failure, severe cardiac valvular disease, a high-grade atrio-ventricular block on EKG, or a symptomatic ventricular arrhythmia or a myocardial infarction within 6 months prior to enrollment.)
13. Any uncorrected visual impairment or abnormality

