14. Self-reported history, current diagnosis of psychosis or symptoms consistent with a mood disorder based upon the Structured Clinical Interview for DSM-5 (SCID); including schizophrenia, mania, bipolar disorder, an eating disorder, obsessive compulsive disorder, major depression (subjects with a history of major depression but in remission for past 6 months are eligible). If a participant screens positive for one of the above mentioned mood or depressive disorders they will be excluded from the study and provided with contact information for local treatment programs (mood referrals document).

TMS-related:

1. Subjects with ferromagnetic material in or in close proximity to the head (with the exception of oral dental devices).
2. Implanted devices (including VNS, DBS, pacemakers, spinal cord stimulators, medication pumps, ventriculo peritoneal shunts, defibrillators, intracardiac lines)
3. Self-report of any skull fracture or opening
4. A disturbance in normal sleep patterns/sleep deprivation

Note: Although there is no known risk of TMS to the fetus, the issue has not been fully addressed. Consequently, pregnant women will be excluded. All women of childbearing potential (as described above) will agree to use a medically accepted method of birth control while enrolled in the study and pregnancy status will be monitored throughout participation with the use of pregnancy screens.

General Exclusion:

1. Any medical condition, illness, disorder, or concomitant medication that could compromise participant safety or treatment, or affect clinical or cognitive outcomes, as determined by the Principal Investigator
2. Inability to complete study tasks and provide quality data, as determined by the Principal Investigator

3. Low or borderline intellectual functioning – determined by a score of less than 90 on the Shipley Institute of Living Scale (SILS) (administered at Intake Visit). The SILS correlates with the Wechsler Adult Intelligence Scale-Revised (WAIS-R) Estimated IQ Test
4. Inability to provide informed consent

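### Pregnancy is an exclusion throughout, but the pregnancy test is run privately, leaves staff without the result, and is followed by advice instead of a stop rule

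*Combined protocol and SAP*

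**What the plan says.** All references are to the combined protocol and SAP.

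**The exclusion.** Key Exclusion Criteria opens with a rule that runs for the whole study: "Subjects who present and/or self-report with the following criteria at any point during study participation will not be eligible". Item 1 of the Medical/Neuropsychiatric list is "Women who are pregnant, planning a pregnancy, and/or breast feeding". The note after the TMS-related exclusions repeats it ("Consequently, pregnant women will be excluded") and adds that "pregnancy status will be monitored throughout participation with the use of pregnancy screens". Vulnerable Populations says "Children (under age 18), pregnant women or prisoners are not included in this research study".

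**The test.** At Intake (Procedures, Intake item 3) the woman runs the test herself, and the accompanying text is: "Participants are advised that we do not recommend participation for pregnant women, and that they may withdraw at any time without penalty". The Urine Pregnancy Test paragraph under Screening/Covariates, which covers the later tests as well, has her "informed that pregnant women are not advised to participate in this research study" and continues: "Participants will then be instructed to administer the pregnancy test independently and will inform study staff if they would like to continue participation". She may stop there without penalty and is still reimbursed for travel.

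**The schedule.** The exclusion criterion, Table 1 (with footnote 3) and the Urine Pregnancy Test paragraph give Intake, Baseline and Sessions 1, 5, 10 and 15. The first and third of these describe the testing as weekly. The TMS Sessions procedure list (item 2) adds Session 20.

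**The concern.** An exclusion decides who may be treated; advice leaves that choice to the participant. The eligibility sections do the first and the test procedure does the second. The test is the plan's named instrument for monitoring pregnancy, yet its result can stay with the woman who ran it.

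Three things are at stake. First, a woman with a positive test who keeps it to herself can go on to stimulation that the plan means to withhold. Second, with no recorded result, the sponsor cannot show that the exclusion was applied or identify an exposed pregnancy, although a birth defect is one of the protocol's serious adverse event categories. Third, the payment structure favours staying: a woman who stops at a test is promised travel money for that visit, while continuing keeps visit pay and the $60 weekly attendance bonuses, within an estimated total of up to $955. Voluntary withdrawal is a weak safeguard under those terms.

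**Working it through.** The plan gives no statistical figure on this point. The check is a comparison of texts, followed by a count.

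**1. What each screen leads to.**
- Drug screen (Screening/Covariates): a positive result other than THC means ineligible. The Alcohol/Drugs exclusions allow one exception at Intake, for patients of the ADHD programme who report stimulant treatment.
- Breath alcohol of 0.01 or more: ineligible at Intake; afterwards the Principal Investigator decides.
- Estimated IQ below 90: ineligible.
- Pregnancy test: the participant says whether she wishes to go on. No consequence of a positive result is stated.

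**2. Whether staff learn the result elsewhere.** Tissue Specimens says urine is collected for the pregnancy screen, and the privacy section lists test results among the data that may be collected. Neither says who reads this test or that the result reaches staff.

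**3. Number of tests per woman of childbearing potential.**
- Intake, Baseline, Sessions 1, 5, 10, 15: 6 tests, of which 4 fall at a visit with stimulation.
- With Session 20: 7 tests, of which 5 fall at a visit with stimulation.

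**4. Weekly coverage.** Table 2 places Sessions 1–5 in week 1, 6–10 in week 2, 11–15 in week 3 and 16–20 in week 4. The six-test schedule therefore has two tests in week 1 (Sessions 1 and 5), one each in weeks 2 and 3, and none in week 4. Session 20, where listed, is the only week 4 test.

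**5. Upper bound on later exposure.** Assumptions: all 20 sessions attended, and the test precedes stimulation within the visit, as in the order of the TMS Sessions list. Sessions from a test at Session s onward = 20 − s + 1. The plan's pulse count reproduces: 80 trains × 5 s × 10 Hz = 4,000 per session.

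| Positive test at | Sessions that could follow | Active-arm pulses (× 4,000) |
|---|---|---|
| Intake, Baseline or Session 1 | 20 | 80,000 |
| Session 5 | 16 | 64,000 |
| Session 10 | 11 | 44,000 |
| Session 15 | 6 | 24,000 |
| Session 20, if tested | 1 | 4,000 |

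If the test came after stimulation, each figure for a test at a TMS session falls by one session. These are ceilings. The top row for an Intake positive needs five later tests (of the six) and 20 pre-session checks all to pass without disclosure. The number of women affected cannot be calculated, because the documents give neither a sex split nor a pregnancy rate.

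**The case against.** The strongest reply is that the test paragraph does not stand alone. Under TMS Training Procedures, an investigator or trained assistant must check before each session that the participant still meets the entry criteria, and pregnancy is one of them. The TMS Safety Checklist, given at Intake and every TMS session, exists to verify continued eligibility. The medical history review at Intake covers the listed contraindications, and Data and Safety Monitoring has staff record clinical data. Contraception is required, and the exclusion is precautionary, since the note states no known risk to the fetus.

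Most of this stands. A reader might infer from the test paragraph that the plan lets a woman known to be pregnant be stimulated if she wishes. The documents do not support that: the whole-study exclusion rule and the pre-session check require staff to stop a woman who discloses. Nor can one infer that the checklist fails to ask about pregnancy, because its items are not in the documents. A reader might also take the pulse totals as a measure of harm. They count stimulation to the left prefrontal cortex and say nothing about fetal risk.

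What does not fall away is the missing link. None of these safeguards refers to the test result. They depend on a woman volunteering what the test procedure has just told her she may weigh for herself. The test adds protection only if its result reaches the people making the eligibility decision.

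**Conclusion.** The point holds in a limited form. The test procedure is inconsistent with the plan's own exclusion, and a woman who does not disclose a positive test can still receive TMS. A woman who does disclose should be stopped by the existing checks.

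Severity is minor to moderate. The expected number is small, though it cannot be computed. No hypothesis test, power statement or analysis is affected; this is a matter of participant safety and documentation. The finding rests on the written procedures, and unpublished checklist items or working instructions could already close part of the gap.

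The schedule discrepancy is minor, but it is not only clerical: the version given in three places leaves week 4 without a test, contrary to the stated weekly frequency.

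**What to change.** 1. In Intake item 3 and the Urine Pregnancy Test paragraph, replace the advisory wording with a rule: a positive test makes the participant ineligible and ends stimulation.
2. Have her report or show the result to staff, who record it before stimulation as part of the pre-session eligibility check and the TMS Safety Checklist. Reporting costs less privacy; showing gives firmer verification. Either removes the contradiction once the rule is stated.
3. Keep the self-run test, the exit without penalty and the travel reimbursement.
4. Use one schedule in the exclusion criterion, the TMS Sessions list, Table 1 and the Urine Pregnancy Test paragraph, with a week 4 test before stimulation: for example at Session 16, or at least at Session 20.

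**Cost.** Amendment wording and one recorded result per test. Every pregnancy-test visit now listed, including Session 20, already has a urine drug screen, so no visit or sample is added there. A Session 16 test would add one urine sample at an existing visit, because no drug screen is scheduled then. The main downside is some loss of privacy. The plan describes the kit as CLIA-waived, and its one sentence on CLIA compliance concerns withholding drug-screen results from participants. Whether recording a self-run result raises a CLIA question cannot be settled from the documents and should be confirmed with the IRB.
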